11.9 Efficacy Analyses

11.9.1 Primary Efficacy Analysis

The primary efficacy analysis will be conducted using the mITT (primary analysis population), ITT and PP populations.

The primary endpoint (clinical cure at TOC) will be analyzed using a Cochran-Mantel-Haenszel row mean scores test stratified by site. Pairwise treatment comparisons of SCY-078 vs. active comparator (fluconazole) will be performed using a Fisher's Exact test; p-values and 95% confidence intervals for odds ratio will be presented. Subjects whose results are missing at Day 10 (TOC) will be imputed as failures in the analysis. A sensitivity analysis will be performed where subjects with missing values will be removed from the analysis.

VSS scores at Baseline, TOC, and FU will be summarized for each sign and symptom using frequency counts and percentages. Summary statistics will be provided for the total VSS composite score (observed value and change from baseline). Student's t-test will be used for pairwise treatment comparisons of SCY-078 vs. fluconazole; p-values and 95% confidence intervals will be presented for the differences between treatment groups.

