10.2 Blinding, Randomization and Stratification

This is a randomized, double-blind, double-dummy study. All site and sponsor personnel will be blinded to treatment assignment, except for a member of the sponsor personnel or a sponsor representative who will be involved in safety activities.

Approximately 180 eligible subjects will be enrolled and randomized in equal allocation (at a 1:1:1:1:1:1 ratio) to one of the 6 study treatment groups (5 experimental groups and 1 active comparator group). For the purpose of maintaining treatment blinding, all randomized subjects will receive matching SCY-078 placebo tablets and/or matching fluconazole placebo capsules as needed based on treatment assignment, in a double-dummy fashion.

All randomization of subjects will be managed electronically through an interactive voice response system (IWRS).

There will be no stratification for this study.

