11.1 Inclusion Criteria

Subjects must fulfill all of the following criteria to be eligible for study admission:

1. Subject is a female subject 18 years and older and is in good general health based on medical history, physical examination, vital sign measurements and safety laboratory tests performed at the Screening visit and/or prior to administration of the initial dose of study drug.
2. Subject has a diagnosis of symptomatic AVVC that meets the following criteria:
 - a. Moderate to severe disease, defined as a minimum composite vulvovaginal signs and symptoms score of ≥ 7 , with at least 2 signs or symptoms having a score of 2 (moderate) or greater in the VSS Scale at Baseline
 - b. Positive microscopic examination with 10% KOH in a vaginal sample collected at Screening revealing yeast forms (hyphae/pseudohyphae) or budding yeasts
 - c. Normal vaginal pH (≤ 4.5)
3. Subject is not pregnant and is highly unlikely to become pregnant since she meets at least one of the following criteria:
 - a. Subject is a female subject who is not of reproductive potential and is eligible without requiring the use of contraception. A female subject who is not of reproductive potential is defined as one who: (1) has reached natural menopause (defined as 6 months of spontaneous amenorrhea with serum follicle-stimulating hormone levels in the postmenopausal range as determined by the local laboratory, or 12 months of spontaneous amenorrhea); (2) is 6 weeks' post-surgical bilateral oophorectomy with or without hysterectomy; or (3) has undergone bilateral tubal ligation. Spontaneous amenorrhea does not include cases for which there is an underlying disease that causes amenorrhea (e.g. anorexia nervosa).
 - b. Subject is a female subject who is of reproductive potential and agrees to remain abstinent or use (or have her partner use) 2 acceptable methods of contraception starting from the time of consent through 28 days after the completion of study therapy. Acceptable

methods of birth control are intrauterine device, condom, hormonal contraceptives and vasectomy.

Hormonal contraception, including but not limited to oral, injectable or implantable methods, are not acceptable as a single method of contraception because the effect of SCY-078 on the efficacy of oral contraceptive pills has not yet been established.

Subjects must refrain from using any vaginal contraceptives as these may have an impact on the signs and symptoms of AVVC.

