10. DATA CONVENTIONS FOR ANALYSIS

10.1 General Statistical Principles

All statistical tests will be performed at the unadjusted 0.05 (two-sided) or equivalently 0.025 (one-sided) level of significance. The study is not powered for formal statistical comparisons.

All observed and derived variables (e.g., change from baseline, response status) used in the summaries of analyses will be presented in by-subject listings. Descriptive statistics will be used to provide an overview of the efficacy and safety results. For categorical parameters, the number and percentage of subjects in each category will be presented. The denominator for percentage will be based on the number of subjects appropriate for the purpose of analysis. For continuous parameters, descriptive statistics will include number of subjects, mean, standard deviation (SD), median, minimum, and maximum.

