11.9.2 Secondary Efficacy Analyses

The secondary efficacy analyses will be conducted using the mITT, ITT and PP populations.

Binary efficacy endpoints (mycological eradication, composite clinical cure and mycological eradication, and continued clinical response at FU) will be analyzed using the same methods/tests as described for the primary efficacy endpoint.

Time to resolution of signs and symptoms after initiation of study drug will be analyzed using Kaplan-Meier methods. Pairwise treatment comparisons of SCY-078 vs. fluconazole will be performed using log-rank test.

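### The planned analysis of clinical cure at TOC does not use the Baseline composite VSS score; the tests are valid, but an adjusted estimate should be pre-specified beside them, for a gain that is modest and rests on assumption

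*SAP*

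**What the plan says.** Clinical cure at TOC requires all six VSS items (three signs, three symptoms) to score 0, with no need for further antifungal treatment (SAP 11.8.1). Two analyses are planned in SAP 11.9.1:

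- Overall: "The primary endpoint (clinical cure at TOC) will be analyzed using a Cochran-Mantel-Haenszel row mean scores test stratified by site".
- Pairwise: "Pairwise treatment comparisons of SCY-078 vs. active comparator (fluconazole) will be performed using a Fisher's Exact test", with a 95% confidence interval for the odds ratio.

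The one sensitivity analysis described there removes subjects with missing results. Protocol 18.7.2 names the same two tests, without the site strata. SAP 11.9.2 says that the binary secondary endpoints "will be analyzed using the same methods/tests as described for the primary efficacy endpoint".

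Protocol 11.1 makes severity an entry condition: "Moderate to severe disease, defined as a minimum composite vulvovaginal signs and symptoms score of" at least 7. Protocol 10.2 says: "There will be no stratification for this study". The SAP uses Baseline VSS for item frequencies, total-score summaries, and change from baseline with t-tests. It is not a covariate for cure, and SAP 11.3 does not list it among the baseline characteristics.

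SAP 10.1 adds: "The study is not powered for formal statistical comparisons". SAP 12 gives any analysis not specified in the SAP unblinded, exploratory status.

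**The concern.** The primary objective is to choose a regimen by comparing efficacy between arms of about 30, fewer in the mITT population. A subject who enters at 7 has less to clear than one who enters at 15, so Baseline VSS plausibly predicts whether every item reaches 0. If it does, leaving it out has two consequences. Each difference from fluconazole is estimated less precisely than the collected data allow. And an arm that happens to draw milder subjects will look better, with no pre-specified estimate that allows for this. The descriptive tables would show such an imbalance, but by then an adjusted analysis would no longer be pre-specified.

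**Working it through.** **There is no plan figure to reproduce beyond the total.** 6 arms × 30 = 180, which matches. No power, effect size or cure rate is stated.

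**Is the covariate available?** Six items scored 0 to 3 give a maximum of 18, and entry requires at least 7. Every eligible subject therefore has a pre-dose composite between 7 and 18.

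**Inputs for the illustration**
- Two-sided 5% level (SAP 10.1) and n = 30 per arm (SAP 3).
- Fluconazole cure 55%. This is an assumption: Protocol 7.1 gives 55% for therapeutic cure, which also needs negative KOH and culture. No clinical cure rate is given.
- SCY-078 cure 85%: an assumption.
- rho, the correlation between Baseline VSS and cure: not in the documents, so taken over 0 to 0.4.

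**Precision by formula**
- Unadjusted SE = √[(0.55×0.45 + 0.85×0.15)/30] = √(0.375/30) = 0.1118.
- Adjusted SE ≈ SE × √(1 − rho²).
- Power = Φ(0.30/SE − 1.96).

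| rho | SE | Power | Gain (points) |
|---|---|---|---|
| 0 | 0.1118 | 76.5% | – |
| 0.2 | 0.1095 | 78.2% | 1.7 |
| 0.3 | 0.1066 | 80.3% | 3.8 |
| 0.4 | 0.1025 | 83.3% | 6.8 |

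The formula takes the whole rho² (4%, 9%, 16%) as a variance cut and charges nothing for estimating the slope.

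**Precision by simulation**
- Six arms, Baseline VSS on 7 to 18 with an assumed SD of about 2.2: variance ratios of 0.97, 0.93 and 0.89 at rho 0.2, 0.3 and 0.4. Adjusted vs unadjusted power was 75% vs 75%, 77% vs 74% and 79% vs 73%. Adjusted type I error was 4.5% to 5.5%.
- Two arms of 30, strength set as an odds ratio for cure per SD of VSS: variance up about 1.5% with no association, down 1-2% at odds ratio 1.5, 7-9% at 2 and 15-19% at 3. The R² values of 0.038, 0.098 and 0.197 correspond to rho = √R² of about 0.19, 0.31 and 0.44.

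The results move with the assumed cure rates and VSS distribution. A fair summary is about 3-4% at rho 0.2, 8% at 0.3 and 13-17% at 0.4.

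**Chance imbalance** (in SDs of VSS, so no SD need be assumed)
- SD of the difference between two arm means = √(2/30) = 0.258.
- P(difference above 0.5 SD), one pair = 2 × [1 − Φ(0.5/0.258)] = 5.3%. For at least one of the five pairs with fluconazole, by simulation: 19%. With an assumed 20 per arm: 11% and 37%.
- A 0.5 SD imbalance moves the unadjusted cure difference by 4.8, 7.7 or 10.9 points at odds ratios of 1.5, 2 and 3 per SD.

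**The planned pairwise test.** By exact enumeration at n = 30, Fisher's test has size 2.7% (both arms 55%) and power 64.5% (55% vs 85%). The unadjusted normal approximation above gives 76.5%, and a pooled z-test gives 72.9%. The gap is 76.5 − 64.5 = 12.0 points, or 72.9 − 64.5 = 8.4 points. Either exceeds the simulated gain from the covariate at rho up to 0.4. Setting the adjusted model's power directly against Fisher's would credit the covariate with a gain that comes mostly from the choice of test.

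**The case against.** The strongest reply is that nothing here is an error. Under randomisation the unadjusted tests keep their nominal error rate, and chance imbalance is already counted in it. A reader might infer that the planned comparisons are biased or invalid. The documents do not support that: the loss is in precision and in how a particular imbalanced result is read.

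Second, no document links Baseline VSS to cure, and the entry floor of 7 narrows its range. A reader might expect gains of 9 to 11 points of power, which appear at rho 0.5. That needs an odds ratio of about 4 per SD of VSS, a gradient for which the documents give no basis. At rho 0.2 to 0.3 the simulated gain is 0 to 3 points.

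Third, the study is described as exploratory and unpowered. This limits the weight of the point. It does not remove it, because the SAP still plans p-values and confidence intervals and the stated aim is to choose a dose.

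Fourth, a reader might conclude that the model should replace the planned tests and cover all binary secondary endpoints. That goes too far. The protocol names the CMH and Fisher tests. Mycological eradication is a culture result with no shown link to VSS. Continued clinical response is defined in subjects already cured at TOC, which is a condition arising after randomisation.

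The first, second and fourth objections stand as limits on size and remedy. The omission itself is not disputed.

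**Conclusion.** The point holds in a limited form. SAP 11.9.1 leaves out a baseline measurement of the scale that defines the primary endpoint, although it exists for every eligible subject and randomisation does not balance it. The cost is some precision and the lack of a pre-specified allowance for chance imbalance in severity, not a loss of validity.

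The benefit of adjustment runs from slightly negative (variance up about 1%) if VSS is not prognostic to a useful but modest improvement at rho 0.4. Every figure rests on the assumed association, and the power figures also rest on the assumed 55% and 85%. The conservatism of Fisher's test is a separate matter and a larger source of lost pairwise power. The change is worth making because it is nearly free now and loses its pre-specified standing after unblinding.

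**What to change.** Before unblinding, add to SAP 11.9.1 one pre-specified adjusted analysis of clinical cure at TOC in the mITT population:

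- **Model:** all six arms together, with treatment group and Baseline composite VSS as a linear term. Use logistic regression with standardisation (Firth penalty if an arm is near 100% cure), or a linear model with small-sample robust standard errors. Choose one in advance.
- **Covariate:** the last non-missing value before the first dose (SAP 10.3). The protocol's schedule has signs rated at Screening but not at a separate Baseline visit, so state that the rule applies to each item before summing.
- **Missing TOC results:** count as failures, as already planned.
- **Report:** adjusted cure rate per arm and adjusted risk difference from fluconazole, with 95% confidence intervals.

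Keep the site-stratified CMH and Fisher tests as planned. Do not extend the model to mycological eradication or continued clinical response.

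The cost is a paragraph of SAP text, a little programming, one model degree of freedom, and about 1% more variance if VSS does not predict cure. No new data, visits or subjects are needed.

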9.3 Exploratory Endpoints

- Percentage of subjects with a negative KOH test at the TOC visit
- Percentage of subjects who are free of signs and symptoms at the FU visit
- Percentage of subjects by *Candida* species infection at Baseline
- Percentage of isolates susceptible to SCY-078 and fluconazole
- Percentage of subjects with clinical cure (complete resolution of signs and symptoms) at TOC by *Candida* species
- Percentage of subjects with mycological eradication (negative fungal culture) at TOC by *Candida* species
- Determination of the PK parameters (C_{max} and AUC) for each dosing regimen and evaluation of the dose/exposure relationship relative to clinical outcome

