18.6.2 Pharmacokinetic Analyses

PK parameters will be estimated using Population PK analysis in NONMEM as detailed in the SAP. The PK analyses will be done using the PK Population.

An evaluation of exposure for each dosing regimen relative to clinical cure will be performed.

The concentration versus time data from the PK samples collected in this study will be analyzed using a Population PK (Pop PK) model to predict AUC and C_{\max} (as appropriate). A Pop PK modeling strategy is required because the sampling time points will not support a standalone PK analysis, and hence, the data from this study will be pooled with data from other oral studies to predict AUC and C_{\max} on Day 1 of treatment. A stand-alone Population PK report will be prepared to describe the analysis performed on the PK samples collected from this study.

Further analysis of possible metabolites may be performed.

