18.7.2 Efficacy Analyses

The efficacy analyses will be conducted using the mITT (primary analysis population), ITT and PP populations. The efficacy parameters will be evaluated comparing each SCY-078 treatment group (and all treatment groups combined) versus the active comparator (fluconazole) group.

The primary endpoint (clinical cure at TOC) will be analyzed using a Cochran-Mantel-Haenszel row mean scores test. Pairwise treatment comparisons of SCY-078 vs. fluconazole will be performed using a Fisher's Exact test; p-values and 95% confidence intervals will be presented. Subjects whose results are missing at Day 10 (TOC) will be imputed as failures in the analysis. A sensitivity analysis will be performed where subjects with missing values will be removed from the analysis.

For continuous efficacy endpoints, the Student's t-test will be used for pairwise treatment comparisons of SCY-078 vs. fluconazole; p-values and 95% confidence intervals will be presented for the differences between treatment groups. For categorical endpoints, Fisher's Exact test will be performed, and p-values and 95% confidence intervals will be presented. The time to resolution of signs and symptoms after initiation of study drug will be analyzed using Kaplan-Meier methods.

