2. STUDY OBJECTIVES

Primary Objective:

- To identify the recommended dose of oral SCY-078 in subjects with moderate to severe Acute Vulvovaginal Candidiasis (AVVC) by comparing the efficacy of different dose levels and dosing regimens of oral SCY-078

Secondary Objectives:

- To evaluate the efficacy of oral SCY-078 in subjects with AVVC based on mycological and clinical outcomes
- To evaluate the safety and tolerability of different dose levels and dosing regimens of oral SCY-078 in subjects with AVVC

Exploratory Objectives:

- To explore the efficacy of SCY-078 in subjects with AVVC based on potassium hydroxide (KOH) testing at the TOC visit
- To explore the efficacy of SCY-078 in subjects with AVVC based on additional clinical outcomes
- To explore the prevalence of Candida species among subjects with AVVC
- To explore the in vitro activity of SCY-078 against baseline Candida spp. isolates
- To explore clinical and mycological outcomes by Candida species
- To evaluate the PK of SCY-078 after oral administration of different dose levels and dosing regimens of SCY-078 in subjects with AVVC

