12. CHANGES FROM THE PROTOCOL AND PLANNED ANALYSES

This SAP reflects the analysis plan outlined in the study protocol without significant change. Any analysis changes or additional analysis not specified in this SAP will have the status of unblinded and exploratory investigations.

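### The primary objective compares SCY-078 regimens with one another, but every planned pairwise efficacy comparison is against fluconazole

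*SAP*

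**What the plan says.** **Objective.** Protocol 8.1 and SAP 2 give the same primary objective: to identify the recommended SCY-078 dose "by comparing the efficacy of different dose levels and dosing regimens of oral SCY-078".

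**Pairwise analyses.** Protocol 18.7.2 sets up efficacy as "comparing each SCY-078 treatment group (and all treatment groups combined) versus the active comparator (fluconazole) group". For clinical cure, SAP 11.9.1 states: "Pairwise treatment comparisons of SCY-078 vs. active comparator (fluconazole) will be performed using a" Fisher's exact test, with intervals for the odds ratio. The same section applies t-tests against fluconazole to the VSS composite score. SAP 11.9.2 carries the primary methods over to the secondary binary endpoints and, for time to resolution, says: "Pairwise treatment comparisons of SCY-078 vs. fluconazole will be performed using log-rank test". SAP 11.9.3 carries the methods over to the exploratory endpoints.

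**Overall test.** Clinical cure is also "analyzed using a Cochran-Mantel-Haenszel row mean scores test stratified by site". Neither document says which arms enter.

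**Exposure.** Protocol 18.6.2 adds: "An evaluation of exposure for each dosing regimen relative to clinical cure will be performed". Protocol 9.3 lists the "evaluation of the dose/exposure relationship relative to clinical outcome" among the exploratory endpoints. SAP 11.11 sends the PK analyses to a separate report.

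**Later additions.** Under SAP 12, any "additional analysis not specified in this SAP will have the status of unblinded and exploratory investigations".

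**The concern.** The contrast named in the objective is regimen against regimen. The contrast analysed is regimen against fluconazole. A team that follows the plan exactly would hold five cure rates, five odds ratios against a common comparator and one overall p-value. It would have no planned statement of how far apart any two regimens are, or how uncertain that gap is.

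Comparisons with a common reference do not fill this gap. One regimen can fall below p=0.05 against fluconazole and another above it when the two are hardly distinguishable from each other. A regimen contrast added after unblinding would be post hoc under SAP 12, although it answers the primary question.

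**Working it through.** **1. Inputs from the documents.** There are six arms allocated equally, five of them SCY-078, with about 30 per arm: 6 × 30 = 180, which matches the stated total. No formal sample size calculation, cure rate, effect size or power is given, so there is no power figure to reproduce. Tests are two-sided at an unadjusted 5%. All cure rates below are assumptions. So is 24 per arm, which supposes that 80% of 30 qualify for mITT.

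**2. Planned comparisons side by side.**

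| Analysis | Contrast | Gives a between-regimen estimate? |
|---|---|---|
| Fisher's exact, clinical cure (SAP 11.9.1) | SCY-078 vs fluconazole | No |
| t-test, VSS score (SAP 11.9.1) | SCY-078 vs fluconazole | No |
| Secondary binary endpoints (SAP 11.9.2) | As for clinical cure | No |
| Log-rank, time to resolution (SAP 11.9.2) | SCY-078 vs fluconazole | No |
| Combined groups (Protocol 18.7.2) | Pooled vs fluconazole | No |
| CMH row mean scores (SAP 11.9.1) | Overall, arms not stated | No, p-value only |
| Exposure vs cure (Protocol 18.6.2) | Method not stated | Not specified |

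SCY-078 pairs: 5 × 4 / 2 = 10. Pairs with a planned difference or interval: 0.

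**3. What the overall test shows.** Unstratified, the row mean scores statistic for a binary outcome is (N − 1)/N × Pearson chi-square. It was simulated with 100,000 or more trials per scenario, all five SCY-078 arms at 55% and fluconazole at 35%, so that no regimens differ:

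| | Six arms | Five SCY-078 arms |
|---|---|---|
| 30 per arm | 28% reject | about 5% |
| 24 per arm | 22 to 23% | about 5% |

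Stratifying over 20 equal sites, in smaller simulations, gives roughly a quarter at 30 per arm and 17 to 19% at 24 per arm for six arms, and again about 5% for five arms. With other assumed gaps at 30 per arm, the unstratified six-arm test rejects in 9 to 10% (55% vs 45%), 19% (70% vs 55%) and 35% (75% vs 55%).

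**4. Why comparisons with fluconazole do not substitute.** Hypothetical counts: regimen A 21/30, regimen B 19/30, fluconazole 12/30.
- Fisher's exact, A vs fluconazole: p = 0.037. B vs fluconazole: p = 0.12.
- A minus B = 0.700 − 0.633 = 0.067.
- Wilson limits: A 0.521 to 0.833, B 0.455 to 0.781.
- Newcombe lower limit: 0.067 − √[(0.700 − 0.521)² + (0.781 − 0.633)²] = −0.165.
- Newcombe upper limit: 0.067 + √[(0.833 − 0.700)² + (0.633 − 0.455)²] = 0.289.

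One regimen passes 5% and the other does not. Yet they differ by 7 points, with an interval from −17 to 29 that the plan would not produce.

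**5. Precision of the missing estimates.** The half-width of a 95% interval for a difference, at 50% cure, is 1.96 × √(2 × 0.25/n): 0.253 at n = 30 and 0.283 at n = 24.

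**6. Is a dose trend a safe substitute?** Total doses are Group 1, 750 mg; Group 2, 2 × 300 = 600 mg; Group 3, 2 × 450 = 900 mg; Group 4, 6 × 150 = 900 mg; Group 5, 6 × 300 = 1800 mg. Simulated power at 30 per arm:

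| Assumed cure pattern, Groups 1 to 5 | Log-total-dose trend | Five-arm overall test |
|---|---|---|
| Linear in log total dose, 45% to 75% | 72% | 48% |
| Plateau above 600 mg (70/50/70/70/70%) | 23% | 33% |
| Follows size of each dose (75/55/65/45/55%) | 9% | 50% |

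The trend does well only if its assumed shape is right.

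**The case against.** The best defence is that the study claims little. It declares itself exploratory and unpowered, and Protocol 7.2 promises only an initial indication of the best regimen, to guide later phases. Cure rates will be tabulated by arm, so anyone can subtract two of them and compute an interval from the counts. No section selects a regimen by its p-value against fluconazole. The overall test is not a fluconazole contrast; if it were run on the five SCY-078 arms it would bear directly on the objective. If it is run on six, rejecting when fluconazole truly differs is correct. An exposure evaluation is also planned, and intervals of about 25 points either side will seldom separate regimens.

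Much of this is fair. The 28% is not an error rate of the six-arm test; it shows only that a rejection need not concern the regimens. The outline of tables in SAP 15 is a bare heading in the text available, so a between-regimen table there cannot be ruled out, though no analysis section provides for one.

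The central point still stands. Exploratory status excuses the lack of powered tests, but the plan already runs unadjusted tests against fluconazole and leaves out the contrast its objective names. A reader's own subtraction is not a pre-specified analysis. The exposure evaluation is exploratory, has no stated method for relating exposure to cure, and rests on sampling in about 10 subjects per arm pooled with other studies. Wide intervals are a reason to show the uncertainty.

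**Conclusion.** The concern holds. On the analysis sections of both documents, none of the 10 SCY-078 pairs has a planned difference or interval, although comparing those regimens is the primary objective. This rests on the text alone and on no assumed rate. The simulated figures are illustrations that depend on assumed cure rates, equal arms and, for 24 per arm, an assumed 80% mITT yield. They show that neither the overall test with fluconazole included nor the comparisons with fluconazole can stand in for a regimen contrast. The defect does not invalidate the trial, since the data will support the right analysis. It should be fixed before unblinding, because afterwards that analysis counts as post hoc under the plan's own rule.

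**What to change.** Before unblinding, amend SAP 11.9.1 and align Protocol 18.7.2:

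- **Regimen differences.** Name, as the analysis addressing the primary objective, the differences in clinical cure between SCY-078 pairs with 95% intervals (for example Newcombe), in mITT with missing TOC counted as failure. Present them as estimates, not tests. Highlight Group 3 vs Group 4 (900 mg total in each, over 1 day vs 3 days) and Group 2 vs Group 5 (same twice-daily dose, 1 day vs 3 days), noting that total dose also differs in the second pair, 600 vs 1800 mg.
- **Overall test.** State which arms enter the planned CMH test, and also run it among the five SCY-078 arms.
- **Fluconazole comparisons.** Keep them as supportive.
- **Optional, exploratory only.** A trend on total dose, or a pooled 1-day vs 3-day contrast. The latter is confounded with dose: mean total (750 + 600 + 900)/3 = 750 mg vs (900 + 1800)/2 = 1350 mg.

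The cost is wording and a few tables, with no new data and no extra patients. The drawback is more exploratory estimates, with intervals of about 25 points either side at 30 per arm and 28 at 24 per arm.

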6. SAMPLE SIZE DETERMINATION

This is an exploratory study and no formal sample size calculation was performed. Approximately 180 subjects will be enrolled and randomized in an equal allocation (at a 1:1:1:1:1:1 ratio) to the six study treatment groups (see Table 1). Thirty subjects per group are estimated to be adequate to perform an initial assessment of the safety and tolerability as well as the potential efficacy of SCY-078 in subjects with AVVC.

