10.3 Baseline and Change from Baseline

Baseline is defined as the last non-missing assessment prior to the date (and time if appropriate) of the first dose of study drug. Change from baseline is defined as: post-baseline value – baseline value.

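### The t-test on total VSS names no form, visit or baseline covariate; ANCOVA on baseline would give one answer per comparison and visit at little or no cost in precision.

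*SAP*

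**What the plan says.** SAP 11.9.1 has three consecutive sentences on VSS.

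- The first is about single items: "VSS scores at Baseline, TOC, and FU will be summarized for each sign and symptom using frequency counts and percentages". This is the only one that names visits.
- The second is about the total: "Summary statistics will be provided for the total VSS composite score (observed value and change from baseline"). This is the only one that names the two forms, and it concerns descriptive statistics.
- The third is the test. Student's "t-test will be used for pairwise treatment comparisons of SCY-078 vs. fluconazole; p-values and 95% confidence intervals will be presented for the differences" between groups. It names no form, visit or covariate.

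The protocol does not settle the matter. Section 18.7.2 and the synopsis say: "For continuous efficacy endpoints, the Student's t-test will be used for pairwise treatment comparisons of SCY-078 vs. fluconazole", again without form, visit or covariate. They do add one comparison that SAP 11.9.1 does not repeat: efficacy is compared with fluconazole for each SCY-078 group and also for the groups combined.

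A baseline value is available. Entry requires moderate to severe disease, "defined as a minimum composite vulvovaginal signs and symptoms score of" at least 7 (Protocol 11.1), and SAP 10.3 fixes which value counts: "Baseline is defined as the last non-missing assessment prior to the date (and time if appropriate) of the first dose of study drug".

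Total VSS is not among the primary, secondary or exploratory endpoints in SAP 11.8, and SAP 10.1 states: "The study is not powered for formal statistical comparisons".

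**The concern.** The plan promises p-values and confidence intervals for total VSS, but a programmer could produce different sets of them from the same text. The observed-value and change-score comparisons estimate the same quantity under randomization. In a given trial they differ by the chance baseline imbalance between the two arms. If both are reported, a reader may see one significant and one not, with no rule for which to rely on. If only one is reported, its interval may be wider than it need be, and which form loses more depends on a correlation nobody yet knows. Adjusting for baseline deals with both problems using data the trial already collects.

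**Working it through.** **No figure to reproduce.** The plan gives no SD, correlation, effect size or power for VSS. SAP 6 gives only the size ("Approximately 180 subjects will be enrolled and randomized in an equal allocation", 180 / 6 = 30 per arm). The mITT size is not stated, so 20 and 15 per arm are assumed as a range.

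**Number of tests.** There are 5 single-group comparisons plus the combined one, 2 forms and 2 post-baseline visits. The wording allows from 5 × 1 × 1 = 5 up to 6 × 2 × 2 = 24 t-tests per population (20 without the combined comparison). With ANCOVA it is 6 × 2 = 12 contrasts.

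**How far the two t-tests differ.** Let B be baseline, Y the post-baseline score, and 1 and 0 the two arms. Then

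(Ȳ₁ − Ȳ₀) − [(Ȳ₁ − B̄₁) − (Ȳ₀ − B̄₀)] = B̄₁ − B̄₀.

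The expected absolute size is 0.798 × s_B × √(2/n). With an assumed s_B = 2.44, this is 0.798 × 2.44 × √(2/30) = 0.50 points at 30 per arm and 0.62 at 20.

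**Why ANCOVA merges them.** Regressing Y − B instead of Y on treatment and B lowers the coefficient of B by 1 and leaves the treatment coefficient unchanged. Observed value and change therefore give the same adjusted difference, standard error and p-value.

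**Precision, closed form.** With SDs s_B and s_T and within-arm correlation r, the variances are proportional to:

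- observed: s_T²
- change: s_B² + s_T² − 2·r·s_B·s_T
- ANCOVA: s_T²(1 − r²)

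| Assumed SDs | Variance ratio | r = 0.1 | r = 0.3 | r = 0.5 |
|---|---|---|---|---|
| any | ANCOVA / observed | 0.99 | 0.91 | 0.75 |
| s_B = s_T | ANCOVA / change | 0.55 | 0.65 | 0.75 |
| s_B 2.5, s_T 2.0 | ANCOVA / change | 0.43 | 0.50 | 0.57 |
| s_B 2.5, s_T 3.0 | ANCOVA / change | 0.65 | 0.76 | 0.87 |
| s_B 2.5, s_T 3.5 | ANCOVA / change | 0.72 | 0.84 | 0.94 |

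The gain over change is the larger of the two only when r < s_B/(2·s_T). With s_B = s_T that is r < 0.50; with s_B 2.5 and s_T 3.0 it is 2.5/6.0 = 0.42.

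**Cost of estimating the slope.** For a two-arm comparison of N subjects the ANCOVA variance is multiplied by 1 + 1/(N − 4), and one degree of freedom is lost. At N = 60 the interval is √1.0179 × t₅₇/t₅₈ = 1.009 times the observed-value interval when r = 0. At 20 and 15 per arm the factor is 1.015 and 1.021. The same factors apply against the change score if the true slope happens to be 1. ANCOVA beats the observed-value test once r exceeds about 0.14, 0.17 or 0.20 at 30, 20 or 15 per arm.

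**Check with a score floored at zero.** Six items scored 0–3 give a total of 0–18. Assumptions: baseline is a rounded normal(10, 3) kept within 7–18 (mean 10.7, SD 2.44); latent TOC SD is 3, 4.5 or 6, with latent r as shown, rounded and cut to 0–18; 30 per arm. Mean 95% interval width with 50% zeros, ANCOVA with HC3 errors:

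| Latent SD, r | Change | Observed | ANCOVA |
|---|---|---|---|
| 4.5, 0.1 | 3.64 | 2.87 | 2.88 |
| 4.5, 0.3 | 3.26 | 2.88 | 2.80 |
| 4.5, 0.5 | 2.82 | 2.91 | 2.60 |

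Share of trials in which the two t-tests fall on opposite sides of 5%:

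| Zeros at TOC in the two arms | Disagreement |
|---|---|
| 70% vs 40% | about 21–44% |
| 60% vs 50% | about 10–17% |
| equal (50%) | about 5–9% |

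With no true difference, at least one of the two is significant in about 7–9% of trials, against 5% for each alone.

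**The case against.** The strongest reply is that nothing here is an error. An unadjusted t-test in a randomized trial is unbiased, total VSS is a supportive summary, the study is exploratory, and the protocol states that no multiplicity adjustment will be made. All of that stands and keeps the point minor. Several stronger readings should be set aside:

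- A reader might infer that the t-test is invalid or biased. The documents do not support that; both forms are valid.
- A reader might infer that the plan commits to 24 tests. It does not say so. Both forms at TOC and FU is the natural reading of the paragraph, but the test sentence leaves it open.
- A reader might take 21–44% as the expected rate of disagreement. It needs an assumed gap of 30 percentage points in zero scores, and the documents give no basis for such a gap.
- A reader might infer that ANCOVA always gains. At low correlation it gains nothing over the observed-value test, and an entry minimum of 7 with a floor at zero tends to lower the correlation.
- A reader might infer that the cure analysis or the dose choice is compromised. The primary analysis is untouched, and no decision rule in either document uses the VSS p-values.

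It is also fair that ANCOVA's linear form suits a score with many zeros no better than the t-test does, and that it departs from the protocol's stated method. What the reply does not answer is that the plan promises a test without saying what it tests.

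**Conclusion.** The point holds as a minor one. The form and visit of the total VSS test are unspecified, and a baseline measured on every eligible subject goes unused. Under the assumed SDs and correlations, ANCOVA is clearly more precise than the change-score test when the correlation is low, and than the observed-value test when it is moderate. Its worst cost is a few percent in interval width near zero correlation. The disagreement rates rest wholly on the assumed score model and on how far the arms differ. The identity of the adjusted result for observed value and change, and the fall from up to 24 tests to 12, rest on no such assumption.

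**What to change.** Replace the t-test sentence in SAP 11.9.1 with text to this effect:

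> Total VSS at TOC, and separately at FU, will be analysed by ANCOVA with treatment (six levels) and baseline total VSS (section 10.3) in subjects with an observed score at that visit. Adjusted mean differences, 95% CIs and p-values will be given for each SCY-078 group and for all SCY-078 groups combined against fluconazole. Observed values and changes will be summarised descriptively.

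The missing-data clause is needed because SAP 8 assigns a failure status to missing visits, which does not supply a score. The combined contrast restores the comparison in Protocol 18.7.2. Robust (HC3) standard errors are optional; they allow for unequal variances and widened the ANCOVA interval by about 1–3% in the simulations.

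Record the change in SAP section 12, which now reports no significant departure from the protocol. The t-test may stay as a supplementary analysis with its form and visit named. If ANCOVA is not adopted, naming the form and visit is the least that should be done.

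Cost: one replaced sentence, one model per visit and one entry in section 12. No new data are needed. The separate unadjusted test of change is lost unless kept as supplementary.
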